MAIN STUDY PROCEDURES	 Randomisation 1 Multi-parametric MRI compared to biparametric MRI Randomisation 2 Targeted biopsy performed using image-fusion targeted and systematic biopsies compared to visual-registration targeted and systematic biopsies in patients with visible suspicious finding on either bpMRI or mpMRI. Duration of follow-up: For up to 12 weeks after enrolment.
OUTCOME MEASURES (PRIMARY ENDPOINTS)	
Randomisation 1	Proportion of clinically significant cancers, defined as any amount of Gleason >/=3+4 (ISUP Grade Group >/=2) on biopsy, detected in the randomised population of patients at risk.
Randomisation 2	Proportion of clinically significant cancers, defined as any amount of Gleason >/=3+4 (ISUP Grade Group >/=2) on biopsy, detected in the randomised population of patients biopsied for a suspicious MRI.
OUTCOME MEASURES (SECONDARY ENDPOINTS)	
	Proportion recommended for biopsy in randomised arm Proportion actually biopsied in each randomised arm

Proportion diagnosed with clinically insignificant prostate cancer (defined as any Gleason 3+3=6 [ISUP Grade Group 1])
Proportion of clinically significant and insignificant cancers using other histological definitions of clinical significance - PROMIS 1 and 2 - any Gleason >/=4+3 [ISUP Grade Group >/=3] - Gleason >/=3+4 [ISUP grade Group >/=2] or any Gleason 3+3 [ISUP Grade Group 1] of >/=6mm - Gleason >/=3+4 [ISUP grade Group >/=2] with >/=10% pattern 4 OR presence of cribriform pattern OR presence of intraductal components
Detection rates for each randomised group of known prognostic risk categories. These are D'Amico, National Comprehensive Cancer Network (NCCN) and Cambridge Prognostic Groups (CPG).
Adverse events and patient reported outcomes
Outcomes by centre stratified by size and type of MRI scanner, route of biopsy and amount of systematic sampling.
Healthcare resource utilisation, costs and cost- effectiveness of using fastMRI compared to mpMRI and image-fusion compared to cognitive targeted biopsies
Consent for linkage to national databases to collect medium and long-term outcomes including new diagnostic tests, prostate cancer diagnoses and treatments, deaths and prostate cancer deaths

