2.5 Summary Table of Objectives and Endpoints

Objectives	Endpoints	Timepoint(s) of evaluation of this endpoint (if applicable)
Primary Objective	As above	Maximum 12 weeks following enrolment
Secondary Objectives	As above	Maximum 12 weeks following enrolment

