Further, we will use risk groups as defined by D'Amico, NCCN and CPG (using the latest versions that are published at the time of the Statistical Analysis Plan being finalised).

Validated patient reported outcome measures

The ProBE PETB questionnaire included: Hospital Anxiety and Depression Scale (HADS) score, and urinary, bowel, and sexual symptoms assessed by using the validated University of California, Los Angeles petb

state Cancer Index questionnaires. The UCLA-PCI questionnaires have now been converted into the Expanded Prostate Index Composite (EPIC).

- We will compose a modified questionnaire to incorporate the latest versions of EPIC into the ProBE questionnaire. So, the questionnaire in IP7-PACIFIC will incorporate the following: HADS, EPIC (Urinary, Erectile and Bowel domains) and the EuroQol (EQ-5D-5L) will be used in the study as a generic measure of health-related quality-of-life which can be linked to public preferences [Janssen et al, 2013].

- Patients will be asked to self-report pain and discomfort (referred to as pain hereafter) immediately after and seven days after biopsy on a 4-point Likert-type scale as none, mild, moderate, or severe. Specific related complications such as fever, flu-like shivers, pain, haematuria, haematochezia, and haemoejaculate will be self-reported at 7-14 days after biopsy (or after MRI if no biopsy carried out) and at 35 to 90 days after prostate biopsy as absent or present following biopsy on a purpose designed questionnaire. For each symptom, patients will be asked to score the degree of "problem" as none, minor, moderate, or major. This will be used to derive a binary outcome for each symptom (present/moderate/severe problem vs. absent /minor problem).

The timepoints for the questionnaires are also referenced in the Patient Reported Outcomes and Experience Questionnaire as follows:

- Hospital Anxiety and Depression Scale (HADS) score questionnaire
 - Time-points: After Consent, 7-14 days after biopsy (or after MRI if no biopsy) and 35-90 days after biopsy
- EPIC (urinary, erectile, bowel)
 - Time-points: After Consent, 7-14 days after biopsy (or after MRI if no biopsy) and 35-90 days after biopsy
- EuroQol (EQ-5D-5L)
 - Time-points: After Consent, 7-14 days after biopsy (or after MRI if no biopsy) and 35-90 days after biopsy
- Questionnaire on MRI related side-effects
 - To be given to all patients to be completed after the MRI but before the biopsy (if they have a biopsy)

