5.2 Screening and pre-randomisation evaluations

Written informed consent will be obtained before the subject undergoes any study related procedures such as screening for eligibility. There are no pre-screening or screening tests required.

Pre-screening log: Collects the number of eligible patients who were given the PIS, provides information regarding the number of drop-outs/withdrawals, the reasons behind why the patients decided not to enrol onto the study and the acceptance rate of the study within the patient population. This activity is included as part of 'approach potential participant to discuss study' within the SoECAT.

Screening log: Collects and tracks details of all the patients with completed informed consent and any reasons for screen failures and patient withdrawals. This activity is included as part of 'informed consent' or as part of any subsequent visits within the SoECAT.

Consent for both randomisations will be sought at the outset to make the study conduct efficient, minimise drop-out and help centres meet NHS 28-day faster diagnosis targets. We intend to follow patients up to a maximum 12 weeks post-enrolment, so we will also collect information about what treatment options are available for patients who have diagnosed prostate cancer and what treatment they chose through multidisciplinary team (MDT) outcomes in the clinical records and clinic letters or entries by clinicians in the health records. Most patients with localised prostate cancer will be able to choose from a number of options that straddle active surveillance, focal therapy, radical surgery or radiotherapy (with some men started on androgen deprivation therapy), depending on cancer risk. Recent NHS guidance in 2019 was changed to allow for patients with intermediate and low risk cancer to take longer than the previous 31/62-day targets permitted so patients' decision about final treatment choice can sometimes take up to 3 months. This means we will be able to collect final treatment decisions for most of our participants with this information collated directly from health records; this information is unlikely to be available prior to database lock for CONFIDENTIAL Page 27 of 55

IP7-PACIFIC Protocol No: 22CX7488	Imperial College London	V3.0 18 th December 2023
-----------------------------------	-------------------------	-------------------------------------

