5.3 Randomisation and Blinding

Biases and blinding

- Randomisation controls for performance and incorporation biases with respect to the clinical utility of bpMRI in comparison to mpMRI.
- Pathologists will be blinded to MRI type by ensuring the pathology request forms do not provide this information.

Imaging scan data

IP7-PACIFIC	Protocol No: 22CX7488	Imperial College London	V3.0 18 th December 2023

Imaging scans are performed as part of this study. We will also ask for consent from patients to store and use their scan data in future research (academic or commercial) to see if new ways of looking at these scans can detect cancer better in the future. All scans need to be electronically transferred for collation at Imperial in order to facilitate double reporting and therefore will be available for data banking within the Research Data Store (https://www.imperial.ac.uk/admin-services/ict/self-service/research-support/rcs/rds/).

Randomisation process

In randomisation-1, patients with suspected prostate cancer will be allocated in a 1:1 ratio to bpMRI or mpMRI, and those with a suspicious MRI (either bpMRI or mpMRI) who are recommended to undergo targeted biopsy will be allocated 1:1 to image-fusion or visual-registration biopsy (along with non-targeted systematic biopsy as per guidance). Randomisation-2 will be stratified for type of MRI to which participants in the first randomisation are allocated.

	Screening			
Visit	1	2	3	4
Week	0	1-8	1-8	2-12
Informed consent	Х			
Inclusion & exclusion criteria	Х			
Demographics	Х			
Targeted medical history	X ¹			
MRI		Х		
Biopsy (in some patients)			X ²	
Patient questionnaires	X ³	X ³		X ³
Biopsy results				X4
Adverse events			X ⁵	X ⁵

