5.5 Follow-up

Any incidental findings should be identified at the study visits and reviewed by the site teams and if necessary will be reported to the clinical care team and subjects GP.

These reflect standard care and there will be no additional follow-up visits required for the study.

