10.4 Data Collection

eCRFs will be based on relevant data collection tools tested in previous studies that we have undertaken and will undergo review by the study team, relevant clinical staff and the statistician prior to use. Patient level data collection will include baseline factors, MRI results, biopsy recommendations, biopsy details and results, adverse events and post biopsy complications. Self-reported, validated patient questionnaires will be used to assess healthrelated quality of life. These will be collected at baseline and once at last follow-up. Details of procedures for CRF/eCRF completion will be provided in a study manual.

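### The protocol contradicts itself on when the late patient-reported questionnaires are due and who receives them

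*Protocol*

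**What the plan says.** **Late time point.** Section 5 (Validated patient reported outcome measures) gives HADS, EPIC and EQ-5D-5L the same schedule: "Time-points: After Consent, 7-14 days after biopsy (or after MRI if no biopsy) and 35-90 days after biopsy". The MRI alternative is attached to the 7-14 day point only. Symptom self-report follows the same pattern: "or after MRI if no biopsy carried out) and at 35 to 90 days after prostate biopsy as absent or present following biopsy". The biopsy side-effect questionnaire goes to biopsied men only, at 7-14 and 35-90 days.

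**End of follow-up.** The trial summary gives the duration as "For up to 12 weeks after enrolment". Section 5.2 says "We intend to follow patients up to a maximum 12 weeks post-enrolment". Section 2.5 gives the evaluation time for both primary and secondary objectives as "Maximum 12 weeks following enrolment". The visit table (between sections 5.3 and 5.4) places consent, MRI, biopsy and the last visit at "Week 0 1-8 1-8 2-12". Section 5.5 adds that "there will be no additional follow-up visits required for the study".

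**Number of collections and recipients.** Section 10.4 says of the validated quality-of-life questionnaires: "These will be collected at baseline and once at last follow-up", with no restriction to biopsied men. The visit table marks questionnaires at Visits 1, 2 and 4 without such a restriction, but its footnote 3 refers back to the section 5 schedule. The section 5 text on men who are not biopsied expects the patient questionnaire to record further tests over the three months of trial follow-up.

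**The concern.** Three things do not fit together. The late window is counted from biopsy, while the end of follow-up is counted from enrolment, and the two clocks can miss each other. Section 5 leaves men without a biopsy with no late time point, while other places read as if every man completes a final questionnaire. Section 5 has two collections after baseline, and section 10.4 has one. A site or the central team cannot satisfy all of these at once.

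Two things are at stake. Late symptoms and quality of life in men biopsied late would either go uncollected or be collected outside the stated follow-up. More important for inference, the proportion biopsied is itself an endpoint of randomisation 1. A late patient-reported comparison confined to biopsied men conditions on an event after randomisation that the type of MRI can change. It would also be blind to any benefit of avoiding biopsy. Data not collected cannot be recovered later in the analysis.

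**Working it through.** **The plan's own figure.** The schedule has no calculated figure to reproduce. The randomisation 1 sample size, which supplies the denominator, does reproduce. With 38% in both arms, a 5% margin, one-sided 0.05 and 90% power, n per arm = (1.645 + 1.282)² × 2 × 0.38 × 0.62 / 0.05² ≈ 1614.1. This rounds up to 1615 per arm, or 3230 in total. Allowing for 10% attrition, 3230 / 0.90 ≈ 3589, consistent with the target of 3600.

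**Inputs for the schedule check.** Enrolment is day 0 and a week is 7 days.
- Follow-up ends on day 12 × 7 = 84 (trial summary, sections 2.5 and 5.2).
- Biopsy falls on day B, in weeks 1-8, so B runs from 7 to 56 (visit table).
- The late window is day B + 35 to day B + 90, which is 56 days (section 5).

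**Does the window fit?**
- It fits in full only if B + 90 ≤ 84, so B ≤ −6. This never happens.
- It fits in part if B + 35 ≤ 84, so B ≤ 49.
- Window days inside follow-up = 84 − (B + 35) + 1 = 50 − B, or 0 if negative.

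| Biopsy day | Late window (days) | Window days by day 84 |
|---|---|---|
| 7 | 42-97 | 43 of 56 |
| 28 | 63-118 | 22 of 56 |
| 49 | 84-139 | 1 of 56 |
| 50 | 85-140 | 0 |
| 56 | 91-146 | 0 |

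The latest window end, day 146, is 146 / 7 = 20.9 weeks after enrolment. By contrast, the 7-14 day point after a day-56 biopsy or MRI is day 63-70, which lies inside follow-up.

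**How many men are biopsied too late?** The protocol gives no distribution of biopsy dates. As an illustration only, if biopsies were spread evenly over days 7-56 (50 days), those on days 50-56 (7 days) could not reach the window: 7 / 50 = 14%. Earlier biopsies would make this share smaller.

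**How many men have no late time point under section 5?** Section 8.1 cites approximately 70-75% recommended for biopsy and assumes 70%. If recommended is taken as biopsied:
- at 70%: 3600 × 0.30 = 1080 (540 per MRI arm);
- at 75%: 3600 × 0.25 = 900 (450 per MRI arm);
- if only 60-65% were actually biopsied (an assumption): 1440 to 1260.

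On the 3230 men required before attrition, 70% gives 3230 × 0.30 = 969.

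**Counting collections.** Section 5 has baseline plus two. Section 10.4 has baseline plus one. The visit table has a single questionnaire column after the biopsy visit (Visit 4) for the two post-biopsy collections in section 5.

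**The case against.** A reader might infer that the MRI arms cannot be compared on patient-reported outcomes, or that non-biopsied men are left out by design. The documents do not support either reading. All men have baseline and 7-14 day HADS, EPIC and EQ-5D-5L, because section 5 supplies the MRI anchor there. Section 10.4, the Visit 4 column and the section 5 text on men not biopsied can all be read as giving every man a final questionnaire. Both section 5 and footnote 3 also point to a separate questionnaire document that is not at hand. The protocol is inconsistent on this rather than clearly omitting these men. Still, the visit table defers to section 5, so section 5 is the schedule most likely to be followed, and it has no late anchor for them.

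A reader might also infer that late data are lost for most men because the 90-day limit never fits. It does not follow. The 35-90 days is a window in which one return suffices, and every biopsy up to day 49 keeps at least one admissible day before day 84. The 28-day diagnosis target in section 5.2 and same-day MRI and biopsy at some centres (visit-table footnote) suggest that many biopsies will come early.

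A biopsy anchor is partly intended. One endpoint in section 2.4 concerns the impact of biopsy in each randomised group, and no objective names a late bpMRI versus mpMRI comparison of patient-reported outcomes. This weakens the point without removing it, since section 2.4 also lists patient-reported outcomes by randomised group.

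The consequences are bounded as well. The cost-utility model takes its EQ-5D utilities from the literature (section 8.3), and section 7.4 requires trial-related safety information to be reported even after a subject has completed the study.

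**Conclusion.** The point holds as an internal contradiction affecting secondary outcomes. The late window is never wholly inside the 12-week limit, is partly inside it for biopsies up to day 49, and is wholly outside it after that. This is arithmetic on the protocol's own figures. The number and recipients of the late questionnaires also differ between section 5, the visit table and section 10.4.

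If section 5 is followed as written, about 900 to 1080 of 3600 men would have no late measure, and a late comparison by MRI arm would be restricted to biopsied men and so would not be a randomised comparison. That count is an order of magnitude: it treats men recommended for biopsy as men biopsied and ignores attrition. The 14% of biopsies too late for the window rests on an assumed even spread and is illustrative only.

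The 7-14 day comparison, the primary endpoints and the sample size are unaffected. The missing MRI anchor does not touch randomisation 2, which excludes men refusing biopsy. The matter should be corrected, but it does not threaten the trial's main conclusions.

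**What to change.** 1. Reconcile the trial summary, section 2.5, section 5 (follow-up of men not biopsied, and the questionnaire schedule), section 5.2, the visit table with its footnotes, and section 10.4, so that they state one schedule and one set of recipients.
2. Define the end of questionnaire and adverse-event collection relative to biopsy, or to MRI if there is no biopsy, so that the late window lies inside follow-up.
3. Send the late HADS, EPIC and EQ-5D-5L to non-biopsied men at the corresponding interval after MRI, so that late outcomes can be compared by MRI arm in all randomised men.
4. Correct section 10.4 to three time points.

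The cost is a protocol amendment, one extra electronic questionnaire for about 1000 men, and a somewhat later last-patient date. No extra visit is needed, because section 5 already provides for electronic completion and central distribution. One limitation remains: biopsied and non-biopsied men would still be measured at somewhat different times from randomisation, which should be acknowledged when the late results are read.

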5.1 Identification and recruitment of patients

Patients referred by their GP to hospital due to a clinical suspicion of prostate cancer (elevated serum prostate specific antigen (PSA), abnormal prostate on rectal examination, or both) and agreeing to undergo a prostate MRI as part of standard care will be approached to participate. Potential participants will be patients who are referred to the respective centre for investigation of their prostate for possible malignancy. The dedicated Recruitment Officer will contact the eligible patients by telephone before the patient is seen in clinic once the local clinical care team has obtained the participants permission for this to occur. The patient will be asked for permission to receive the literature pertaining to the IP7-PACIFIC study including REC approved PIS, ICF and contact information for the research team. All patients will have the opportunity to discuss all aspects of the study with their GP, family members, and their Recruitment Officer prior to the clinic appointment at their participating centre but given before consenting to the study. Consent can be obtained remotely using a consent form on the RedCap database with a unique identifier given to the patient. Remote consent with the patient printing out a paper version of the ICF and scanning or posting it back to the trials team is also acceptable. Written or electronic consent can also be taken at a face-toface visit.

5.2 Screening and pre-randomisation evaluations

Written informed consent will be obtained before the subject undergoes any study related procedures such as screening for eligibility. There are no pre-screening or screening tests required.

Pre-screening log: Collects the number of eligible patients who were given the PIS, provides information regarding the number of drop-outs/withdrawals, the reasons behind why the patients decided not to enrol onto the study and the acceptance rate of the study within the patient population. This activity is included as part of 'approach potential participant to discuss study' within the SoECAT.

Screening log: Collects and tracks details of all the patients with completed informed consent and any reasons for screen failures and patient withdrawals. This activity is included as part of 'informed consent' or as part of any subsequent visits within the SoECAT.

Consent for both randomisations will be sought at the outset to make the study conduct efficient, minimise drop-out and help centres meet NHS 28-day faster diagnosis targets. We intend to follow patients up to a maximum 12 weeks post-enrolment, so we will also collect information about what treatment options are available for patients who have diagnosed prostate cancer and what treatment they chose through multidisciplinary team (MDT) outcomes in the clinical records and clinic letters or entries by clinicians in the health records. Most patients with localised prostate cancer will be able to choose from a number of options that straddle active surveillance, focal therapy, radical surgery or radiotherapy (with some men started on androgen deprivation therapy), depending on cancer risk. Recent NHS guidance in 2019 was changed to allow for patients with intermediate and low risk cancer to take longer than the previous 31/62-day targets permitted so patients' decision about final treatment choice can sometimes take up to 3 months. This means we will be able to collect final treatment decisions for most of our participants with this information collated directly from health records; this information is unlikely to be available prior to database lock for CONFIDENTIAL Page 27 of 55

IP7-PACIFIC Protocol No: 22CX7488	Imperial College London	V3.0 18 th December 2023
-----------------------------------	-------------------------	-------------------------------------

many patients recruited and biopsied in the last 3 months of recruitment, so the eCRF will reflect this but given the size of the study is unlikely to have an impact on these findings.

Participants will be asked consent to collect long-term healthcare information from national records (i.e., Office for National Statistics, NHS Digital, Office for Health Improvement and Disparities, and/or other applicable NHS information systems, or national databases) and through a direct approach from the research team at any timepoint within 10 years of consent. We will ask patients to give permission to be contacted by a member of the central / local study research team within 10 years of signing their consent form, after the study has ended to complete a questionnaire about their health status (including details of any other tests and treatment they have had since the study) and quality of life. If the patient decides to take part a member of the study research team may send this request to the patient's home address.

If funding can be successfully obtained for this longitudinal data collection, it will allow us to determine whether patients had further diagnostic tests, prostate cancer diagnosis and its risk (stage, grade, PSA level), as well as any subsequent treatments and cancer-related outcomes (progression, metastases, cancer-related mortality).

If Funding is successful for longitudinal data collection, an amendment submitted via the HRA will be necessary.

Health Status

At the screening visit, patients will also be asked to give consent for identifiable data to be linked with the national databases (ONS and HES database). The identifiable fields (NHS number) required for linkage will be encrypted using a one-way encryption algorithm. We will ask patients if they are happy to give consent for their health status to be followed up over time. This will be done by linking the patient's identifiable data with records held by the NHS and maintained by the NHS Information Centre and the NHS Central Register, or any applicable NHS information system. This will allow us to track what happens after the study finishes and observe if anyone gets further tests/investigations, a diagnosis of cancer in future and its risk (stage, grade, PSA level) and the treatment they have had.

As prostate cancer is often a slow-growing disease which may not develop or progress for many years we will also ask patients to give consent for us to keep personal data stored or accessed for an additional 10 years on the NHSCR (National Health Service Care Register) so that data from national registries can be evaluated. For instance, long-term survival information to be flagged through national registries, for example NHS Digital (previously the Health and Social Care Information Centre); Office of National Statistics (ONS) in England/Wales; General Register Office in Scotland; Hospital Episode Statistics (HES) or Office for Health Improvement & Disparities.

